Relevant Adverse events	
 Time to treatment cessation is defined as the length of time between initiation of first-line treatment and documented disease progression (or start of subsequent LOT, if disease progression is not well documented in patient medical record), treatment discontinuation or switch to another treatment (defined as change from 1 treatment regimen to another). Time to treatment cessation will be calculated from the date of initiation of LOT to the date of disease progression, treatment discontinuation or switch. Patients with no disease progression, treatment discontinuation or switch to another treatment will be censored at the earliest of: date of last medical record entry, last day of the observation period or date of death.
Cause of death (for deceased patients)	
 Information on relevant AEs during the study period will be collected based on information available in the patient medical records. Relevant AEs will be mapped into the (MedDRA) and grouped by SOC and PT. 
Relevant AEs are defined as AEs leading to first-line treatment switch, dose adaptation or discontinuation, or leading to death.

Reasons for treatment discontinuation or switch	
 The primary cause of death will be recorded as available in the medical record (cancer-related, non-cancer related, unknown/missing). Reasons for treatment alteration, defined as treatment interruptions, switches and discontinuation, will be collected at the end of each treatment, based on information available in the patient medical records.

¹ For patients in whom disease progression is not well documented, the start date of subsequent LOT will be considered instead of the date of disease progression. Detailed derivation of LOT will be provided in the SAP.

CR: complete response; ICD-10: International Classification of Diseases 10th Revision; mCRC: metastatic colorectal cancer; MedDRA: Medical Dictionary for Regulatory Activities; LOT: line of therapy; ORR: overall response rate; OS: overall survival; PD: progressive disease; PFS: progression free survival; PR: partial response; PT: preferred term; SOC: system organ class.

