First-line treatment in patients with mCRC includes a combination of chemotherapy regimens and biological agents.^{3 4} Systemic anti-cancer therapy (SACT) is the main treatment option where combination chemotherapy remains the consensus standard of care. Current guidelines advocate the doublet combinations with oxaliplatin (5-fluorouracil [5-FU], leucovorin, and oxaliplatin [FOLFOX]) or irinotecan (5-FU, leucovorin, and irinotecan [FOLFIRI]) based regimens.² These regimens are shown to be superior to combination of 5-FU and folinic acid alone.²⁴

Targeted therapy, including vascular endothelial growth factor (VEGF) inhibitor bevacizumab or epidermal growth factor receptor (EGFR) monoclonal antibodies (cetuximab and panitumumab), is currently recommended by clinical guidelines as selective addition to the chemotherapy regimens, taking into account patient's RAS status.² Bevacizumab, when given in combination with chemotherapy has shown to significantly improve overall survival (OS) compared to chemotherapy alone.^{5 6} The survival benefit was retained in patients who continued using bevacizumab as a combination therapy, beyond first-line progression.⁷ Other biological agents such as cetuximab and panitumumab, both of which are EGFR monoclonal antibodies, have demonstrated benefits in survival, progression free survival (PFS) and response rate when used as first-line treatment of patients with wild-type KRAS (KRASwt) tumors in combination with FOLFIRI and FOLFOX when compared to chemotherapy alone, but not with other oxaliplatin-based regimens such as FLOX

(combination of fluorouracil, leucovorin and oxaliplatin) and CAPOX (combination of capecitabine and oxaliplatin).³⁻⁸

B-Raf proto-oncogene mutant colorectal cancer

BRAF encodes a serine/threonine protein kinase belonging to the RAS/RAF/mitogen activated protein kinase (MEK)/extracellular signal-regulated kinase (ERK) kinase pathway that has been implicated in pathophysiology proliferation, invasion, and metastasis in CRC.²⁵ Approximately 5% to 15% of CRC patients have a mutation in the BRAF gene resulting in a valine-to-glutamate change at the residue 600 (V600E), which is nearly always mutually exclusive with the RAS mutation.^{6-9,26}²⁷ Multiple clinical trials suggest that BRAF mutation is a poor prognostic factor for mCRC.^{10,12,28,29}

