2.2 SECONDARY OBJECTIVES

The secondary objectives are:

1. To describe the baseline demographic and clinical profiles of BRAF^{V600E} mutant mCRC patients receiving first-line treatment, overall and by treatment regimen
2. To describe PFS in BRAF^{V600E} mutant mCRC patients receiving first-line treatment, overall and by treatment regimen
3. To describe OS in BRAF^{V600E} mutant mCRC patients receiving first-line treatment, overall and by treatment regimen
4. To describe treatment response in BRAF^{V600E} mutant mCRC patients receiving first-line treatment, overall and by treatment regimen
5. To describe treatment duration (i.e., time from treatment initiation to treatment cessation) in BRAF^{V600E} mutant mCRC patients receiving first-line treatment, overall and by treatment regimen
6. To describe BRAF mutation testing procedure and timing in regards with the first-line treatment in BRAF^{V600E} mutant mCRC patients
7. To describe the frequency of relevant AEs in BRAFV600E mutant mCRC patients receiving first-line treatment, overall and by treatment regimen. Relevant AEs are defined as AEs leading to first-line treatment switch, dose adaptation or discontinuation, or leading to death.

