3.3 STUDY OUTCOMES

3.3.1 Primary endpoint

The primary endpoints are first-line SACT treatment patterns in BRAF^{V600E} mutant mCRC patients, described by:

- Agent or combination of agents received
- Duration of treatment
- Maintenance therapy (if any)

The first-line SACT regimen(s) will be described from the time of treatment initiation (for mCRC) until the time of first documented disease progression, treatment discontinuation or switch, whichever is earlier.

LOT definition will be connected to treatment progression. The LOT will be defined using a data-driven approach. In the SAP an algorithm for LOT definition will be specified, which will consider the specific treatment(s) received (stop and start dates), progression (as recorded in the patient medical record, including date), documented reasons for discontinuation of treatments and gap(s) between subsequent treatment regimens.

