3.3.2 Secondary endpoints

1. Description of the demographic and clinical profile of patients at the time of treatment initiation (for mCRC)
2. PFS, defined as the length of time between initiation of first-line treatment for mCRC and the first documented disease progression (if disease progression is not well documented in a patient's medical record, then the start of the subsequent LOT may be considered as proxy for disease progression) or death (whichever is earlier)
3. OS, defined as the length of time between first-line treatment initiation (for mCRC) and death (due to any cause)
4. ORR, defined as complete response (CR) or partial response (PR), described at the end of first-line treatment for mCRC
5. Time to treatment cessation, defined as the length of time between initiation of firstline treatment for mCRC and documented disease progression (or start of subsequent LOT, if disease progression is not well documented in the patient medical record), treatment discontinuation or switch to another treatment (defined as change from 1 treatment regimen to another treatment regimen, e.g. change from FOLFOX-based regimen to FOLFIRI or irinotecan-based regimen)
6. Time to BRAF mutation testing since mCRC diagnosis and since first-line treatment for mCRC, and description of testing procedures
7. Frequency of relevant AEs during first-line treatment for mCRC. Relevant AEs are defined as AEs leading to first-line treatment switch, dose adaptation or discontinuation, or leading to death.

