3.3.4 Exposure definition and measurement

This is a NIS of real-world treatment practices in the adult BRAF^{V600E} mutant mCRC patient population. This protocol does not recommend the use of any specific treatments, and no study medication will be provided as part of participation in the study.

The exposure of interest will be the first-line SACT (monotherapy, doublet therapy, or triplet therapy with or without a targeted therapy [either VEGF inhibitor or EGFR inhibitor]) for the treatment of BRAF^{V600E} mutant mCRC. Treatment patterns will be described by LOT.

Line of therapy will be defined as follows:

- First LOT: the start of first LOT will be defined as the first administration of SACT therapy after diagnosis of mCRC to the date of first documented disease progression
- Second and subsequent LOTs: mCRC treatment(s) received on or after the date of documented disease progression following previous LOT to the date of documented disease progression on or after the current LOT
- In the absence of information on disease progression, an algorithm will be specified in the SAP based on the specific treatment(s) received (stop and start dates), progression (as recorded in the patient medical record, including date), documented reasons for discontinuation of treatments and gap(s) between subsequent treatment regimens.

The exposure variables of interest are described in Table 1.

Table 1 Study Exposure

Exposure	Definition and Measurements
Systemic anti-cancer therapy (SACT) ¹ for mCRC	
 Details on SACT (by LOT) 
 LOT² (e.g., first, second, third, etc.) Type of treatment³ (i.e., monotherapy, doublet therapy, triplet therapy) Agents used 
 Chemotherapy regimens (e.g., FOLFOX, FOLFIRI, FOLFOXIRI) Targeted agents (e.g., bvacizumab, cetuximab, panitumumab) Duration of treatment: start date and stop date Date of documented progression Dates and reasons for treatment alteration (e.g., switch, discontinuation, dose escalation/reduction) Maintenance therapy (if any) of first line treatment: name of agent(s); start date and stop date Treatment response (as recorded in patient medical record by the treating physician) of first-line treatment of mCRC: type of response (CR, PR, PD); date recorded

¹ All SACT treatments received/prescribed for mCRC will be captured.

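### Time to treatment cessation is a composite of progression, discontinuation or switch with on-treatment death censored, so it is not the treatment duration named in secondary objective 5

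*Combined protocol and SAP*

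**What the plan says.** Section 2.2, objective 5: "To describe treatment duration (i.e., time from treatment initiation to treatment cessation", to be reported overall and by regimen.

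Section 3.3.2, endpoint 5, starts "Time to treatment cessation, defined as the length of time between initiation of firstline treatment for mCRC and documented disease progression" and then adds discontinuation and switch. The start of the next line stands in for progression where progression is poorly documented. Table 2 in Section 3.3.5 repeats this: "Time to treatment cessation will be calculated from the date of initiation of LOT to the date of disease progression, treatment discontinuation or switch". Anyone without such an event "will be censored at the earliest of: date of last medical record entry, last day of the observation period or date of death".

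Other parts of the protocol set the end of first-line treatment differently:

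- Table 1 (Section 3.3.4) measures duration of treatment by start and stop date and does not mention progression.
- Section 3.3.1 describes first-line regimens "until the time of first documented disease progression, treatment discontinuation or switch, whichever is earlier". Duration of treatment is one component of this primary endpoint. The synopsis version of the window leaves out switch.
- The LOT rule in Section 3.3.4 runs first line from the first administration of systemic therapy "after diagnosis of mCRC to the date of first documented disease progression". Second and later lines are "mCRC treatment(s) received on or after the date of documented disease progression following previous LOT".

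On treatment past progression, Section 1 says of bevacizumab: "The survival benefit was retained in patients who continued using bevacizumab as a combination therapy, beyond first-line progression". It gives no frequency for BRAF V600E-mutant patients.

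**The concern.** The objective names a length of treatment, whereas the endpoint records the first of several events, one of which is not the end of treatment. A patient who stays on the same regimen after documented progression is recorded as having ceased on the progression date, although the actual stop date is in the eCRF. A patient who dies on treatment has plainly finished treatment but is handled as if it would have gone on.

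Duration by regimen is a stated output, and the rationale says that results may support health technology assessment submissions. A reader of a curve labelled treatment duration would take it as drug exposure. Because the primary endpoint also includes duration of treatment, the absence of a single end date reaches beyond objective 5.

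**Working it through.** The plan states no figure for time to treatment cessation. Table 5 concerns regimen shares only and plays no part here.

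**Step 1: ordering.** For one patient let G be the time to documented progression, C the time to actual stop or switch, and D the time to death.

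- Planned endpoint: event at min(G, C), censored at D if D comes first.
- Time on treatment: min(C, D).

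Since min(G, C) ≤ C, the planned time can never exceed the time to actual stop or switch. It is strictly shorter only when G < C, that is, when the regimen continues past progression. This needs no assumption. Where D comes before both G and C, treatment ended at D but the plan censors there. Kaplan-Meier then describes cessation as if on-treatment death did not occur, and so sits above the distribution of min(C, D). The two departures act in opposite directions.

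**Step 2: illustration of size.** The documents give neither the share treated past progression nor the on-treatment death rate. The assumed inputs are:

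- G exponential with median 6 months. Section 1 cites first-line PFS of 6.4 and 5.4 months in BRAF-mutant disease; this is used for scale only.
- Stop or switch for other reasons: exponential with median 12 or 24 months.
- A share f continues the same regimen past progression for an exponential extra time of mean 1.5 or 3 months; the rest stop at progression.
- On-treatment death hazard of 0, 0.02 or 0.05 per month, independent of the rest.

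The planned median follows in closed form:

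- Other-stop median 12: hazard ln2/6 + ln2/12 = 0.1155 + 0.0578 = 0.1733, so median ln2/0.1733 = 4.0 months.
- Other-stop median 24: hazard 0.1155 + 0.0289 = 0.1444, so median 4.8 months.

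Independent censoring at death leaves these medians unchanged. With f = 0 and death counted as the end, the median is ln2/(0.1733 + 0.05) = 3.10 months or ln2/(0.1444 + 0.05) = 3.57 months at the higher death hazard.

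For f > 0, simulation of 400,000 patients per scenario gives these medians in months, with simulation noise of about 0.02. Ranges are for a mean extension of 1.5 to 3 months.

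| Other-stop median | Death hazard | Censored at death under the plan | Planned median | Time on treatment, f = 0 | f = 20% | f = 50% |
|---|---|---|---|---|---|---|
| 12 | 0 | 0% | 4.0 | 4.00 | 4.22–4.34 | 4.53–4.93 |
| 12 | 0.02 | 10% | 4.0 | 3.58 | 3.78–3.88 | 4.03–4.37 |
| 12 | 0.05 | 22% | 4.0 | 3.10 | 3.27–3.35 | 3.49–3.73 |
| 24 | 0 | 0% | 4.8 | 4.81 | 5.07–5.28 | 5.46–6.02 |
| 24 | 0.02 | 12% | 4.8 | 4.23 | 4.45–4.62 | 4.77–5.24 |
| 24 | 0.05 | 26% | 4.8 | 3.57 | 3.74–3.87 | 4.03–4.33 |

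With no on-treatment deaths and f of 20–50%, the planned median is about 5–20% too short: from (4.22 − 4.01)/4.22 = 5% to (6.02 − 4.78)/6.02 = 21%. With 10–26% of patients censored at death, the net error runs from about 0.4 months too short (5.24 − 4.81) to about 1.2 months too long (4.81 − 3.56).

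**Step 3: consistency.** Table 2 ends the interval at progression, discontinuation or switch. The LOT rule ends first line at progression only. Table 1 uses the stop date. The synopsis and Section 3.3.1 differ over switch. The endpoint therefore equals neither the length of first line nor time on drug. Under the LOT rule, an unchanged regimen continued past progression can also appear as second-line treatment in exploratory objective 2.

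**The case against.** The strongest defence is that objective 5 concerns first-line treatment and the LOT rule ends first line at progression. Drug given afterwards is then not first-line duration, and cutting at progression is deliberate. This stands as a reason why the composite may be kept. It does not make the composite a treatment duration: the LOT rule has no end at discontinuation or switch, and Table 1 has no end at progression.

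Three stronger readings are tempting, and the documents do not support them.

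- A reader might infer that the endpoint understates treatment duration overall. That holds patient by patient for those treated past progression. Censoring of on-treatment deaths works the other way, and Step 2 shows that either sign is possible.
- A reader might infer that the endpoint largely repeats PFS. The two coincide where progression comes first, but PFS counts death and this endpoint censors it, while discontinuation and switch are events only here. With earlier stops allowed, the planned median is 4.0–4.8 months against an assumed 6 months to progression.
- A reader might infer from the bevacizumab statement that continuation past progression is to be expected, and that comparisons by regimen are therefore distorted. The statement does not say that the partner chemotherapy stayed the same. If it changed, the switch event ends the interval in any case. Distortion by regimen is possible but not shown.

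Scale also matters. With a planned median of 4.0 months, 300 patients and no censoring, the 95% half-width of the median is about 1.96 × 0.5/(0.0866 × √300) = 0.65 months, where 0.0866 = 0.5 × 0.1733 is the density at the median. Many of the illustrated errors lie within that. The endpoint is descriptive, with no hypothesis test.

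**Conclusion.** The point holds as one of definition and labelling. Time to treatment cessation is a composite of progression, discontinuation or switch with on-treatment death censored. It is neither the duration that objective 5 names nor the start-to-stop duration in Table 1. It is too short for every patient who stays on an unchanged regimen after documented progression, and that part rests on ordering alone.

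The net direction and size for the whole cohort are unknown, because the documents give neither the share treated past progression nor the on-treatment death rate. The illustrated range, about 1.2 months too short to about 1.2 months too long, depends on assumed exponential times, continuing shares of 0–50% and death hazards of 0–0.05 per month. If nobody continues past progression and nobody dies on treatment, the error is zero.

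The change is worth making because the label invites a reading as exposure, the primary endpoint shares the ambiguity, and the dates needed are already collected.

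**What to change.** - In the synopsis, Section 3.3.2 and Table 2, define time to treatment cessation from the systemic therapy dates: permanent stop of all first-line agents or switch to a new regimen, with death on treatment counted as the end of treatment. Use progression or next-line start only to date cessation when the stop date is missing.
- If the composite is kept because first line ends at progression under Section 3.3.4, rename it *time to progression, discontinuation or switch* and report start-to-stop duration beside it, overall and by regimen.
- Use one end date for duration of treatment in the synopsis, Section 3.3.1, Table 1 and Table 2.
- State in Section 3.3.4 that an unchanged regimen continued past progression is not counted as a new line. Otherwise the same drug would fall in both first-line duration and second line.

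No new data are needed: Tables 1 and 4 already collect start and stop dates, and Section 3.8.1 has the SAP written before database lock. The cost is one extra Kaplan-Meier summary if both quantities are reported, plus a small change to the LOT wording.

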3.3.6 Confounding variables

Multivariable analysis will be performed adjusting for baseline covariates in this study. Covariates of interest include patient demographics and clinical profile, and treatment history of CRC, which will be assessed before or at the time of mCRC diagnosis. The baseline covariates are summarized in Table 3.

Table 3 Study Covariates

Covariates	Definition
Age	Age in completed years at the time of first-line treatment for mCRC (will be computed from the date of birth and date of diagnosis of mCRC)
Gender	Male, female
Weight	Weight in kilograms
Height	Height in centimeters

Covariates	Definition
BMI (kg/m ²)	Calculated using weight and height values BMI categories: <18.5, 18.5 - <25, 25 - <30, 30 - <35, ≥35 and unknown/missing
Tests/investigations related to mCRC diagnosis/treatment	
 Records (along with the relevant test dates) of the radiologic, histologic and laboratory tests during the time of diagnosis and follow-up will be extracted based on available information in patient medical records. 
 Tumor Biomarker Assessments (tumor sample or ctDNA): BRAF; RAS; MSI; MMR Blood biomarker assessments: C-reactive protein; carcinoembryonic antigen; carbohydrate antigen 19-9
TNM stage at initial diagnosis	
 Tumor/node/metastasis (TNM) stage (I, II, III, IV) at the time of initial diagnosis of CRC will be abstracted based on available information in patient medical records.
Histology and location of the primary tumor at initial diagnosis	
 Histology at the time of initial diagnosis of CRC will be abstracted based on available information in patient medical records: 
 Adenocarcinoma Other carcinoma Location of the primary tumor: 
 colon left colon right colon transverse rectum
Metastasis status	Metastasis status will be abstracted based on available information in patient medical records: 
 Synchronous or Metachronous Location: Liver, lungs, lymph nodes, bone, peritoneum, CNS, other location(s), unknown Number of metastatic sites
Treatment history	Prior medications/therapies for CRC (where available in patient medical records): 
 Radiation therapy: site of radiation, start and stop date, intent Chemoradiation: concurrent or sequential, regimen, start and stop date Surgery: date, location, intent
Comorbidity profile	Comorbidities of interest: ischemic cardiac disorder, congestive heart failure, peripheral vascular disease, cerebrovascular disease, chronic pulmonary disease, diabetes mellitus with end-organ damage, moderate or severe renal disease, moderate or severe liver disease, rheumatic or connective tissue disease, acquired immunodeficiency syndrome (AIDS), treated hypertension, heart rhythm disorder, others

Covariates	Definition
Performance status	
 • Performance status will be evaluated by ECOG: 
 ○ 0=Fully active, able to carry on all pre-disease performance without restriction ○ 1=Restricted in physically strenuous activity but ambulatory and able to carry out work of a light or sedentary nature, e.g., light house work, office work ○ 2=Ambulatory and capable of all self-care but unable to carry out any work activities. Up and about more than 50% of waking hours ○ 3=Capable of only limited self-care, confined to bed or chair more than 50% of waking hours ○ 4=Completely disabled. Cannot carry on any self-care. Totally confined to bed or chair 
ECOG performance status will be collected at mCRC diagnosis

Biological parameters	
 • Routine laboratory tests at the mCRC diagnosis

BMI: body mass index; BRAF: B-Raf proto-oncogene; CNS: central nervous system; CRC: colorectal cancer; CRP: C-reactive protein; ctDNA: Circulating tumor DNA; ECOG: Eastern Cooperative Oncology Group; LOT: line of therapy; mCRC: metastatic colorectal cancer; MSI: microsatellite instability; MMR: mismatch repair; TNM: Tumor, Node, Metastasis.

